## **9.5 STUDY SIZE**

A feasibility assessment was conducted in June 2020. The results showed that there were approximately 1561 elderly AIS patients who were treated with IV rt-PA and 1037 patients who were admitted to the hospital within 4.5 hours of symptom onset without IVT contraindication and did not receive reperfusion treatment from Jan 2017 to Mar 2020 according to the ZSQCC platform database.

A meta-analysis of RCTs showed that the 3-month favourable outcome (mRS 0-1) with IV rt-PA versus the placebo arm in patients above 80 years of age was 19.1% versus 13.1% (relative risk [RR]: 1.46). In safe implementation of thrombolysis in upper time window monitoring study, the 3-month favourable outcome for IV rt-PA treated elderly patients was 26.6%. In this study, we assume the 1-year favourable outcome for IV rt-PA treated elderly patients is 28%, with the same RR (1.46) observed in RCTs, and the 1-year favourable outcome for non-reperfusion cohort is 19.2%. With the treatment ratio 2:1 between the IV rt-PA cohort and the non-reperfusion cohort, 1106 patients in total are needed to detect the treatment difference of 8.8% with 90% power and a 2-sided alpha of 0.05. Considering a 15% rate of loss to visit, 1301 patients in total are needed. If a 2:1 match cannot reach good match in terms of the major potential confounders, we may conduct a 1:1 match instead. Considering a treatment ratio 1:1 with the same assumption described above with power of 90% at a 2-sided, 974 patients are needed to detect 8.8% treatment difference, considering 15% loss to visit, 1146 patients are needed in total.

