### **9.7.1 Main analysis**

To account for potential confounding, the study cohorts (patients who received IV rt-PA and patients who did not receive reperfusion treatment) will be 1:1 or 1:2 matched by baseline characteristics using the PSM method. The PSM aims to balance the 2 treatment cohorts on baseline covariates. The feasibility of PSM will be evaluated based on available sample size and descriptive results. If patient characteristic between the 2 cohorts are significantly different, i.e., less than 50% of patients in the IV rt-PA cohort can be matched to the non-reperfusion cohort based on PSM, the study design will be re-evaluated before proceeding to analysis. The Nearest Neighbour method of PSM will be used to select the matched samples. The final list of baseline characteristics in the PSM will be decided in conjunction with BI. All variables listed in the covariates will be considered. Covariates including duration of hospitalization and reasons for untreated with rt-PA are only for descriptive analysis. The distribution of baseline characteristics will be presented before and after the matching process. Absolute standardized difference (ASD) between the compared groups will be calculated, in which a  $\geq 10\%$  ASD will be considered a meaningful difference. For baseline covariates that are not sufficiently balanced after PSM which is assessed using ASD, the covariates will be included in an appropriate multivariate model to adjust for those differences.

For the primary outcome, a comparison of 1-year mRS 0-1 score between the 2 propensity score (PS)-matched cohorts will be calculated using a chi-square test. A logistic regression model will be used to calculate odds ratios between 2 matched cohorts.

For the secondary outcomes, descriptive summaries will be conducted in the PS-matched cohorts separately. For categorical variables including any ICH during hospitalisation, mortality during hospitalisation, and mRS 0-2 at 1 year, the percentage and 95% confidence interval will be calculated. A logistic regression model will be used to calculate the odds ratios.

For time to death up to 1 year and time to ICH during hospitalisation, a Kaplan-Meier curve will be used to analyse the data. Cox regression will be used to estimate hazard ratio for 1-year all-cause mortality between PS-matched cohorts.

For the distribution of mRS, an ordinal logistic regression model will be used to calculate the odds ratio between the PS-matched cohorts.

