7. RESEARCH METHODS

7.1 STUDY DESIGN

This is a NIS based on existing data. We will analyse data of AIS patients aged > 80 years in China collected from the ZSQCC platform. [\[P2104780\]](#), [\[P2104783\]](#), [\[P2104784\]](#), [\[P2104779\]](#), [\[P2104782\]](#)

At least 1301 or 1146 AIS patients in total are planned to be enrolled to this study, calculated by 2:1 or 1:1 treatment ratio, respectively.

[figure not shown]
Patients meeting the inclusion/exclusion criteria will be divided into 2 cohorts:

- IV rt-PA cohort: AIS patients aged > 80 years who received IV rt-PA within 4.5 hours of symptom onset
- Non-reperfusion cohort: AIS patients aged > 80 years who arrived or admitted to the hospital within 4.5 hours of symptom onset and did not receive any reperfusion treatments

Propensity score matching (PSM) will be used to match the baseline characteristics between the above 2 cohorts. Clinical outcomes and baseline characteristics will be compared between the matched cohorts.

The flow of data selection for each of the 2 reporting patient cohorts is depicted in [Figure 1](#) below.

Figure 1 Patient cohorts selected for the non-interventional study

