To account for potential confounding, the 2 cohorts will be 1:1 or 2:1 matched by baseline characteristics using the Propensity Score Matching method. The feasibility of PSM will be evaluated based on available sample size and descriptive results. If patient characteristic between the 2 cohorts are significantly different, i.e., less than 50% of patients in the IV rt-PA cohort can be matched to the non reperfusion cohort based on PSM, the study design will be re-evaluated before proceeding to analysis. The PSM aims to balance the 2 cohorts on baseline covariates. The propensity score model will include age, gender, baseline NIHSS/NIHSS categories (0-4, 5-10, 11-15, 16-21, and ≥ 22), medical insurance status, smoking status, hospital level, diabetes, coronary artery disease, atrial fibrillation, prior stroke/transient ischaemic attack, hypertension, anti-platelet, lipid lowering, oral anticoagulation, and time from symptom onset to hospital admission. The method of Nearest Neighbour matching will be used (a maximum caliper width equal to 0.2 of the standard deviation of the logit of the propensity score) to select the matched samples. Then we will compare the baseline characteristics of the 2 propensity-score-matched cohorts. The absolute standardized difference (ASD) between the 2 PS-matched cohorts will be calculated, where at least 0.1 ASD will be considered a significant difference. For baseline covariates that are not sufficiently balanced after PSM, they will be included in an appropriate multivariate model to adjust for those differences.

For the primary outcome, a comparison of the percentage of 1-year* mRS score (0-1) between the 2 PS-matched cohorts will be conducted using a Chi-square test. A conditional logistic regression model will be used to estimate odds ratios (95% confidence interval) between the 2 matched cohorts.

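### Must the 50% matching trigger name its match ratio, given that it asks for about twice as many matched controls at 1:1 as at 2:1?

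*SAP*

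**What the plan says.** SAP 11.1 permits 1:1 or 2:1 matching and then gives the trigger: "If patient characteristic between the 2 cohorts are significantly different, i.e., less than 50% of patients in the IV rt-PA cohort can be matched", the design is re-evaluated before the analysis goes ahead. Just before it stands a separate check: "The feasibility of PSM will be evaluated based on available sample size and descriptive results". Protocol 9.7.1 has the same threshold ("less than 50% of patients in the IV rt-PA cohort can be matched to the non-reperfusion cohort based on PSM") but describes the ratios differently: the cohorts "will be 1:1 or 1:2 matched by baseline characteristics using the PSM method".

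Protocol 9.5 fixes the direction of the ratio: "With the treatment ratio 2:1 between the IV rt-PA cohort and the non-reperfusion cohort, 1106 patients in total are needed". It reports "approximately 1561 elderly AIS patients who were treated with IV rt-PA and 1037 patients who were admitted to the hospital within 4.5 hours" of onset, and it offers a fallback: "If a 2:1 match cannot reach good match in terms of the major potential confounders, we may conduct a 1:1 match instead". SAP 7.1 adds the size requirement: "At least 1301 or 1146 AIS patients in total are planned to be enrolled to this study".

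In the text available, neither document says at which ratio the 50% is counted, whether it is checked again after a move to 1:1, whether controls may be reused, or whether an incomplete 2:1 set counts.

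**The concern.** The trigger is meant to detect cohorts too unlike each other to compare. The share of rt-PA patients matched is not a pure measure of likeness, however. It also depends on the ratio and on the relative cohort sizes. There are fewer controls than rt-PA patients, so a 1:1 match must leave many rt-PA patients out even if the two cohorts are identical, while a 2:1 match can use nearly all of them. One fixed 50% is therefore a much stiffer test at 1:1.

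The ratio is also chosen after match quality has been seen. Cohorts could pass at 2:1, be moved to 1:1 because balance was poor, and then be declared too different. At stake is whether the design is reviewed before the analysis, and whether two analysts with the same data would reach the same decision.

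**Working it through.** **Inputs.** Protocol 9.5: 1561 rt-PA and 1037 non-reperfusion patients; 2:1 means two rt-PA patients per control; favourable outcome 28% versus 19.2%; 90% power, two-sided 5%; 15% loss. SAP 11.1: nearest neighbour, caliper 0.2 SD of the logit propensity score. Assumed, because the documents are silent: no replacement and, for the ceilings and lines, complete sets.

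**1. The plan's own sizes.** The two-proportion formula with pooled variance and no continuity correction gives 976 at 1:1 (stated 974) and 1107 at 2:1 (stated 1106). Then 974/0.85 = 1146 and 1106/0.85 = 1301. The stated sizes reproduce to within rounding.

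**2. Ceilings for identical cohorts.**
- 1:1: 1037/1561 = 66.4% of rt-PA patients.
- 2:1: 780 sets use 1560 of 1561, about 100%.

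**3. Controls needed to reach the line.** 0.5 × 1561 = 780.5, so 781 rt-PA patients.
- 1:1: 781 controls; 781/1037 = 75.3%.
- 2:1: 781/2, rounded up, is 391 controls; 391/1037 = 37.7%.
- Ratio: 781/391 = 2.0. Between 391 and 780 fully matched controls, the rule passes at 2:1 and fails at 1:1.

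**4. Set beside the size targets.**
- 1:1: 1146/2 = 573 pairs, and 573/1561 = 36.7%. A match of full planned size still prompts a review.
- 2:1: 1301 × 2/3 is about 867 rt-PA patients, and 867/1561 is about 55.6%, which clears the line. That is about 434 sets, more than 391, so at 2:1 the size target is the tighter of the two checks.

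**5. Does the verdict reverse?** This needs a propensity score distribution, which the documents do not give, so the simulation is illustrative only. Assumptions: normal logit scores with equal SD, 1561 and 1037 patients, greedy nearest neighbour in random order, 0.2 SD caliper. Share of rt-PA patients matched:

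| Separation | Counting rule at 2:1 | 1:1 | 2:1 | Review prompted at |
|---|---|---|---|---|
| 1.2 SD (c-statistic 0.80) | control takes both partners at once | about 44% | about 63% | 1:1 only |
| 1.2 SD | one partner per round, incomplete sets kept | about 44% | about 63% | 1:1 only |
| 1.2 SD | one partner per round, incomplete sets dropped | about 44% | about 38% | both |
| 0.8 SD | one partner per round, incomplete sets dropped | about 54% | 47–49% | 2:1 only |

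The reversal appears, vanishes or changes direction with a counting rule that the plan leaves to the analyst. If an rt-PA patient counts as matchable whenever at least one control lies within the caliper, about 98% qualify at 1.2 SD whatever the ratio.

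**6. The 1:2 label.** Read as one rt-PA patient to two controls, at most 518 rt-PA patients could be matched (1037/2, rounded down), and 518/1561 = 33.2%. The trigger would then fire even for identical cohorts. Read as controls to rt-PA patients, it is the 2:1 of Protocol 9.5 and the SAP.

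**The case for a change.** The strongest case for a change is that this is the only numerical comparability gate before the main comparison, that the SAP promises fuller detail on matching in particular, and that naming a ratio and a denominator would take two sentences and no new data. A gate whose height depends on a discretionary choice of ratio is less objective than it looks. Even where the simulated reversal vanishes at one separation, it reappears in the opposite direction at another, so dependence on the ratio is real.

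Most of this stands as description: the ceilings and control counts are correct, and the text does not settle the ratio. It falls short as grounds for a change on three counts.
- The sequence of passing at 2:1 and failing at 1:1 is inferred. The fallback is optional, and no visible text orders a second check.
- If the line is re-applied after the switch, the stiffer test meets cohorts whose 2:1 match was already judged poor. A review there is hardly perverse.
- A ratio-neutral rule needs a new threshold. At 75% of achievable matches the lines are 778 pairs and 585 sets; at 50% they are 519 pairs and 390 sets. The first keeps today's 1:1 line and raises the 2:1 line by half; the second keeps the 2:1 line and lowers the 1:1 line by a third. Nothing in the documents favours either.

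**Conclusion.** No change to the plan follows. The wording is incomplete, but analysts can fill the gap sensibly: count the share on the match to be analysed and report how many of each cohort were matched. The documents already provide for showing baseline characteristics before and after matching, flagging standardised differences of 0.1 or more, and adjusting for covariates left unbalanced. Comparability therefore does not rest on the 50% line alone.

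The size of the issue is 781 against 391 controls needed (75.3% against 37.7% of 1037), given the feasibility counts, no replacement and complete 2:1 sets. That factor of two is firm under those assumptions; a reversed verdict is not, because it turns on the handling of incomplete sets and the meaning of matchable. The consequence is confined to whether a review takes place. No effect estimate, test or sample size figure is altered. The 1:2 in Protocol 9.7.1 is clerical and cannot mislead once read beside Protocol 9.5 and SAP 11.1.

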11.3 SAFETY ANALYSIS

This is a NIS based on existing data. From safety information collecting and reporting perspective, this study will not involve individual medical record review, thus no adverse event/adverse drug reaction information is required to collect. The analysis refers to Section 10.1.

Proprietary confidential information © 2021 Boehringer Ingelheim International GmbH or one or more of its affiliated companies

12. QUALITY CONTROL

The statistical analytic approach and programming code will be reviewed/repeated by a second analyst.

